Methods: Double-blind randomized clinical trial conducted in pediatric patients with newly diagnosed or relapsed acute lymphoblastic leukemia. The subjects will be randomized to designate them in the control group (Group1 placebo) or intervention group (Group 2 zinc). The zinc/placebo intervention will be administered orally in tablets of 50-100 mg/day, from day 1 of chemotherapy until the end of the consolidation phase (2 to 2.5 months). For the detection of OM will be used the mucositis scale of the World Health Organization and the observation times will correspond to day 1, 4, 7, 14 and 21 of each chemotherapy cycle. Patients in both groups with OM will receive the same treatment (mouthwash with Gelclair®) and will be observed daily until healing to determine the days of recovery.

Statistical analysis: Independent t-test and Chi-square test for the difference between the two study groups, ANOVA to compare the groups with respect to the severity of OM.

BACKGROUND

The leukemias are a heterogeneous group of neoproliferative processes that are characterized by a clonal expansion of transforming hematopoietic precursors cells, this infiltrate a bone marrow and invade a peripheral blood and other organs.¹ The leukemias has been classified principally by their duration in: acute or chronic and by their cell type are affected in: myeloid, lymphoid and monocytic.² The acute leukemias (AL) are the more frequent type of neoplasia in the childhood and are approximated 33% of malignance pediatric illness.¹

Acute lymphoblastic leukemia (ALL) represents 75% of all cases, being more frequent between 2 and 5 years of age.¹ The worldwide incidence of all types of ranges from 2.0 to 3.5 cases per 100,000 inhabitants per year, while in Mexico 6/100 000 inhabitants are estimated per year;³ so that Mexico is considered to be one of the countries with a high incidence and mortality rate in LA.⁴ The ratio of Lymphoid/myeloid leukemia is 6:1.⁵ In a study on the frequency of acute childhood leukemia in Mexico City, it was found that the National Institute of Pediatrics presented 27.6% of all cases, followed by the Pediatrics Hospital of Mexico "Federico Gomez" with 20.2%.⁶

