Exclusion criteria. Patients with another disease or systemic condition in addition to ALL. Presence of oral infections such as candidiasis, herpetic gingivostomatitis, reactive oral lesions. Children with Down syndrome, patients allergic to zinc or mannitol.

Elimination criteria: Patients who present with hypersensitivity to zinc or placebo (mannitol), those who develop a systemic condition that modifies their treatment or prevents oral care, as well as patients requesting to leave the study.

Definition of the variables

INTERVENTION VARIABLE				
	CONCEPTUAL DEFINITION	OPERATIONAL DEFINITION	TYPE	MEASUREMENT
ZINC	Trace element found in most of the body's cells, having catalytic, structural and cellular regulation functions.	Food supplement based on zinc sulfate in doses of 50-100 mg / day for prevention and treatment of oropharyngeal mucositis .	Qualitative Nominal	1. Apply 2. No apply

DEPENDENT VARIABLES				
ORAL HYGIENE	Combination of physical and chemical measures to control the formation of bacterial plaque, which is the most important risk factor in the development and evolution of caries and periodontal disease.	Oral hygiene registered with the O'Leary index (bacterial plaque on dental surfaces identified by a developer. It is obtained from the sum of stained dental surfaces / total surfaces, multiplied by 100.	Qualitative Ordinal	1. Good 0% to 15%: 2. Regulate 16% to 49%: 3. Poor: 3.50% to 100%:
OM RECOVERY DAYS	Days in which some degree of OM is clinically observed until healing.	Number of days from the clinical diagnosis of OM (Grade ≥ 1) to recovery of the oral epithelium.	Continuous	1,2 ,3 4, 5...

INDEPENDENT VARIABLES

ORAL MUCOSITIS	Inflammatory reaction that affects the entire gastrointestinal tract from the mouth to the anus caused by chemo and / or radiotherapy.	Inflammatory reaction of the oropharyngeal mucosa to chemotherapeutic drugs, according to the WHO scale.	Qualitative Ordinal	Grade 0. Healthy Grade 1. Erythema Grade 2. Ulcers Grade 3. Extensive ulcers Grade 4. Ulcers and necrosis.
PAIN	Localized and subjective sensory perception that is the result of an excitation or stimulation of specialized sensory nerve endings.	Visual scale of facial expressions	Qualitative Ordinal	0-2 No pain 3-4 Mild 5-6 Moderate 7-8 Intense 9-10 Maximum

SOCIODEMOGRAPHICAL VARIABLES

	CONCEPTUAL DEFINITION	OPERATIONAL DEFINITION	TYPE	MEASUREMENT

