AGE	Life time elapsed from birth to the current date.	Life time in years recorded in the clinical record.	Quantitative Discreet	Years 0 a 18
SEX	Physiological and sexual characteristics with which men and women are born.	Biological characteristics recorded in the clinical file as female and male.	Qualitative Nominal Dichotomous	1. Female 2. Male

CONFUSORY VARIABLES				
ACUTE LEUKEMIA LYMPHOBLASTICS (LAL)	Neoplastic disease that results from a clonal proliferation of lymphoid precursors (lymphoblasts), which infiltrates bone marrow, produces a variable degree of pancytopenia and can compromise different organs and / or systems.	Type of leukemia recorded in the clinical file according to the immunophenotype.	Qualitative Nominal	1. Pro B leukemia 2. Common leukemia 3. Pre-B leukemia 4. Mature leukemia B 5. T leukemia (precursors) 6. T leukemia (mature)
NEUTROPENIA	Reduction of peripheral blood neutrophil count .	Absolute neutrophil count obtained by laboratory test (blood count).	Qualitative Ordinal	0. Absence of neutropenia 1. Mild: 1,000-1,500 / ml 2. Moderate: 500-1,000 / ml 3. Severe: <500 / ml
OPPORTUNIST INFECTIONS	Infections in immunosuppressed patients, whether of bacterial, fungal or viral origin.	Record of suggestive lesions by C. albicans and determination by means of KOH, suggestive lesions of herpes and determination by PCR, suggestive bacterial lesions and detection through cultures.	Qualitative Nominal	0. Absent 1. Fungal 2. Bacterial 3. Viral

STUDY DESIGN

Double blind clinical trial

Sampling: Sequential non-probabilistic until the required number of participants is completed.

Randomization: sealed envelopes for group assignment.

Sample size calculation

Formula for the difference of proportions (incidence of OM).

$$\frac{[Z_{\alpha} \sqrt{2\pi_1(1-\pi_1)} - Z_{\beta} \sqrt{2\pi_1(1-\pi_1) + 2\pi_2(1-\pi_2)}]^2}{(\pi_1 - \pi_2)^2}$$

Assumptions:

$$\alpha = 0.05$$

$$\text{Power} = 0.90$$

Rambod study findings: The effect of zinc sulfate on prevention, incidence, and severity of OM in leukemia patients undergoing chemotherapy.

$$Z_{\alpha} = 1.96$$

$$Z_{\beta} = -0.84$$

$$n = 86$$

$$\pi_1 = 75\%$$

$$\pi_2 = 47\%$$

$$\pi_1 - \pi_2 = 28\%$$

$$\frac{[1.96 \sqrt{2(0.75)(0.25)} - (-0.84) \sqrt{(0.75)(0.25) + 2(0.47)(0.53)}]^2}{(0.75 - 0.47)^2} = 46$$

41/5000

15% losses = 53 patients per group

Statistical Analysis Plan

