Descriptive statistics will be used to characterize the population using measures of central tendency and dispersion for continuous variables and distributions of relative and absolute frequencies for categorical variables. Independent t-test and Chi-square test for the difference between the two study groups. Analysis of variance (ANOVA) to compare the two groups with respect to the OM in the five time periods.

METHODOLOGY

Randomization

The randomization will be taught by [name] [name], assigned to the Oncology service, who is unaware of the objective of the study.

The randomization technique will be carried out through sealed envelopes, which will indicate the bottle that will correspond to the patient, identified as treatment "A" and "B". Likewise, to ensure that the groups are balanced, blocks of 6 sealed envelopes containing 3 patients will be made for each group.

Blinding

The patient and the investigator will be blinded; for this, the 50 mg zinc and placebo tablets will be similar in size, color, shape, weight and taste; the bottles will be classified into codes A and B, which in turn will have the same shape, size and color. All of the above will be done through the Pharmaceuticals GREMAR S.A. de C.V., which is a Mexican company that has a line of food supplements located in Mexico City.

An independent investigator (who will be blinded for the purpose of the study) will be requested to receive the medications (zinc / placebo) prepared by the Pharmaceuticals GREMAR S.A. of C.V., so that it provides to the principal investigator only the bottles coded as "A" and "B". At the end of the intervention, the independent investigator will be asked to reveal the coding of the medications to determine which group (Group 1 placebo or Group 2 zinc) corresponds to treatment A and B respectively.

Instruments

WHO OM scale

The oral mucositis scale proposed by the World Health Organization (WHO) in 1979 will be used. This instrument was designed based on objective signs (erythema or ulcer) and subjective signs (mucosal sensitivity, ability to swallow).

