The classification includes 5 degrees as follows: grade 0, no changes in the oral cavity are detected; grade I, pain and erythema in mucosa, gums, tongue or palate; grade II, erythema and ulcers, still with a solid diet tolerance; grade III, oral ulcers, tolerance to pasty foods and liquid diets; and grade IV, ulcers, erythema, pain, inability to swallow fluids, impossible oral feeding, and narcotic requirement to relieve pain. The total score of this scale ranges from 0 to 4.

Visual scale of facial expressions

This scale was developed by Bieri in 1990 for use in children from 3 years. It is made up of faces with different expressions that represent a person who is happy because they do not feel pain, and it changes to a sad expression as the pain increases. Each face is assigned a score, to answer it, the patient is asked to select the face that best describes how he feels.

Standardization

It will be carried out through a series of clinical cases with clinical photographs of different degrees of OM, evaluated using the WHO's OM scale and contrasting the answers with an expert researcher in OM ([name] [name]).

The master's student and a social service student will be standardized, the evaluation will be in pairs and independently.

The weighted Kappa coefficient (k_p) for the degrees of OM will be calculated, until a minimum of 0.61 to 0.80 is obtained.

Stages of the study and data collection

The recruitment of patients will be carried out in the Oncology service of the National Institute of Pediatrics and the Children's Hospital of Mexico. Every day you will wonder if a new patient arrived with suspected leukemia or relapse. We will be aware of the result of the bone marrow aspirate confirming the diagnosis of ALL or relapse.

The master's student will present indicating that the reason for their vision is to inform them about the importance of oral health with respect to their current medical treatment and will give them information about the oral care that they should perform for the prevention of oral complications secondary to their disease and / or the drugs they will receive during their treatment. Visual material will be displayed by means of a computer / tablet device that includes information on oral care indicating brushing technique and making mouthwashes with bicarbonate solution. Likewise, it will explain what consists of

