oropharyngeal mucositis, how it relates to chemotherapy and the preventive measures they can perform. Finally, the complications that may occur during the OM will be explained, such as: difficulty in eating, speaking or swallowing, as well as the measures that must be taken to allow adequate recovery.

Parents will be invited to participate in the protocol explaining the objectives of the study, as well as its risks and benefits. In case of accepting to participate, informed consent and assent (in children over 12 years old) will be presented in accordance with the characteristics that are written in it.

The intervention will be assigned under the balanced block scheme. Children will be randomly assigned to each of the two treatment groups using sealed envelopes.

Oral examination, staining of dentobacterial plaque will be performed (the characteristics of the plaque revealing solution are described in the researcher's manual) for the determination of the oral hygiene index and explanation of brushing technique on day 0 of chemotherapy.

Patients who require dental caries treatment will be rehabilitated by the stomatology service according to their stomatological diagnosis and their general condition. A closed bottle containing 100 tablets (treatment A or B) will be provided according to the random assignment. It will be indicated to administer 1 or 2 tablets daily (according to the age of the patient) from day 1 of chemotherapy.

A written reminder will be provided to parents in which they must check each day if the tablet was taken.

Calls will be made every 3 days to verify that oral hygiene and tablet administration are being carried out; In addition, the reminder will be reviewed twice a week and the remaining tablets will be counted in the bottles.

During the course of chemotherapy (induction and consolidation phase) reviews will be performed on days 1, 4, 7, 14 and 21 of each cycle.

Maneuver

Group 1 (oral care + placebo): gentle tooth brushing with a soft bristle brush 3 times a day and mouthwash with baking soda after each meal (1/4 tablespoon of baking soda dissolved in water to make a mouthwash for 3 minutes) plus the consumption of 1 or 2 oral placebo tablets (mannitol) from day 1 of chemotherapy.

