Six randomized patients with a recent diagnosis of childhood cancer who start chemotherapy will be selected, data from the clinical record will be obtained to determine if it meets the inclusion criteria. The patient identified as eligible will be visited at his place of hospitalization or in the outpatient office of the Oncology Service.

The intervention will be assigned under the balanced block scheme. Children will be randomly assigned to each of the two treatment groups using sealed envelopes.

The sequence of procedures and the complete description of the instruments can be found in the Annex "Pilot test applicator manual".

[figure not shown]
Information collection method

A data record sheet will be filled out that includes the patient's identification form (name, age, sex), type of ALL, chemotherapy phase and blood count; which will be obtained from the clinical file. It will also include the table for the determination of the WHO OM scale, the oral hygiene index and the opportunistic infection registry.

Registration and processing method.

[figure not shown]
The data will be recorded in an Epidata database and analyzed using the STATA 14 statistical program.

FLOWCHART 1

In the previous study by Rambod et al. (12), a difference in the incidence of OM of 28% was obtained and from this, for the present study the estimated sample size was 106 subjects.

Complying with one of the principles that govern clinical trials, which is to reduce the risk of the operated subjects to the minimum possible, in case of observing adverse reactions the suspension of the study will be indicated; while if there are no complications, recruitment will continue until a sample size of 53 subjects is met and at this point the intermediate analysis will be performed as shown in Flowchart 2.

ETHICAL CONSIDERATIONS

In accordance with the principles and guidelines established by good clinical practices (BPC), in accordance with the principles set forth in the Helsinki Declaration of 1964 and with the support provided in the General Health Law, in the Regulations of the General Health Law in the area of provision of Health Care Services, which establishes that the individual welfare of the subjects must sometimes prevail in a study, over the interests of science and the community.

This study will be carried out with the strict observation of the recognized scientific principles and respect, handling the affected data anonymously and confidentially.

Consent

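### Rater calibration by one weighted kappa does not test the grade 0 v grade 1 cut on which OM incidence depends, and no incident-case rule guards against false positives over repeated examinations

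*Combined protocol and SAP*

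**What the plan says.** The sample size calculation in the Study design section compares two proportions, OM incidence of 75% v 47%. It arrives at 46 per group and then "15% losses = 53 patients per group".

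No section defines an incident case. The only threshold sits inside the recovery-time variable in the Definition of the variables table: "Number of days from the clinical diagnosis of OM (Grade ≥ 1) to recovery of the oral epithelium". That table gives grade 1 as erythema alone. The WHO scale text under Instruments gives it as pain together with erythema.

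Under Stages of the study and data collection, "reviews will be performed on days 1, 4, 7, 14 and 21 of each cycle", over an intervention of 2 to 2.5 months. The number and length of cycles are not stated. The Summary adds that children with OM "will be observed daily until healing to determine the days of recovery".

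Under Standardization, two students grade clinical cases with photographs showing various degrees of OM, and their answers are compared with an expert's. The weighted kappa "for the degrees of OM will be calculated, until a minimum of 0.61 to 0.80 is obtained". The weights, the mix of grades and any separate target for grade 0 v grade 1 are not given. No reliability check during the trial is described.

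**The concern.** Incidence at a threshold of grade 1 is decided at the softest boundary of the scale, between a healthy mouth and a mildly reddened one. A weighted kappa over five grades gives partial credit for errors of one grade and takes most of its value from telling mild from severe disease. It can therefore be high while the 0/1 cut is read badly. A minimum expressed as a range adds to this, since 0.61 appears to pass.

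Repetition makes a small error rate matter. A child who never has OM is examined many times, and if one false grade 1 reading is enough, the chance of at least one grows with each visit. Under double blinding these errors should be equally likely in both arms. They raise both incidences, shrink the difference towards zero and could hide a real effect of zinc.

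**Working it through.** **1. The plan's own figure.** The substituted formula gives [1.96·√(2·0.75·0.25) + 0.84·√(0.75·0.25 + 2·0.47·0.53)]² / 0.28² = (1.200 + 0.696)² / 0.0784 = 45.8, so 46 per group; 46 × 1.15 = 52.9, so 53. The stated power is 0.90, but a Z of 0.84 corresponds to 80%; that is a separate matter. With 46 evaluable per group, the pooled standard error is √(2·0.61·0.39/46) = 0.1017 and the unpooled one is √((0.1875 + 0.2491)/46) = 0.0974. Then z = (0.28 − 1.96·0.1017)/0.0974 = 0.83, which is power of 79.6%. This is the baseline below.

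**2. What the kappa can miss.** Assume five equally frequent grades, every grade 0 image read as grade 1, and all else correct. The rater's marginal proportions are then 0, 0.4, 0.2, 0.2 and 0.2.
- Linear weights: observed disagreement 0.2 × 1/4 = 0.05; expected (0.4·1.4 + 0.2·1.2 + 0.2·1.4 + 0.2·2.0)/4 = 0.37; kappa = 1 − 0.05/0.37 = 0.86.
- Quadratic weights: observed 0.2 × 1/16 = 0.0125; expected (0.4·3 + 0.2·2 + 0.2·3 + 0.2·6)/16 = 0.2125; kappa = 1 − 0.0125/0.2125 = 0.94.
- Grade 0 v 1 or more, unweighted: observed and expected agreement are both 0.8, so kappa = 0.

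If this rater also misreads 20% of grades 1-3 and 10% of grade 4 by one grade, the scores are 0.77 and 0.90. With 40% grade 0 images as well, they are 0.68 and 0.87. All of these pass 0.61.

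**3. Build-up over examinations.** Let f be the false-positive rate per examination (assumed; the documents give none) and k the number of examinations. With independent errors and a single-reading rule, a child free of OM is called a case with probability F = 1 − (1 − f)^k. Each observed rate is p + (1 − p)F, so the difference becomes 28 × (1 − F). One cycle gives k = 5; assuming two to three cycles gives k = 10 to 15.

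Example, f = 5% and k = 10: F = 1 − 0.95^10 = 0.401; rates 0.850 and 0.683; difference 16.8 points. Pooled standard error 0.0882, unpooled 0.0865; z = (0.168 − 1.96·0.0882)/0.0865 = −0.06; power 48%.

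| f | k | OM-free children called cases | Difference (points) | Power, 46 per group |
|---|---|---|---|---|
| 2% | 5 | 9.6% | 25.3 | 73% |
| 2% | 10 | 18.3% | 22.9 | 66% |
| 2% | 15 | 26.1% | 20.7 | 59% |
| 5% | 5 | 22.6% | 21.7 | 62% |
| 5% | 10 | 40.1% | 16.8 | 48% |
| 5% | 15 | 53.7% | 13.0 | 36% |

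**4. Correlated errors.** With a beta-binomial model, f = 5% and within-child correlation 0.3, the share falsely called is 20% (k = 10) or 23% (k = 15). The difference is then 22.5 or 21.6 points and power 65% or 62%.

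**5. Effect of confirmation.** If grade 1 must be seen twice and errors are independent, the rate per examination becomes f². At f = 5%, F = 1 − (1 − 0.0025)^k = 2.5% (k = 10) or 3.7% (k = 15), leaving 27.3 or 27.0 points and power of 78% or 77%. This is the best case, because redness misread one day may be misread the next.

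**The case against.** A reader might infer that false positives will erase much of the zinc effect. The documents do not support that, for these reasons.
- **Error rate.** None is given. A lenient kappa limit permits errors at the 0/1 cut but does not show that they occur. The rater in step 2 is an extreme case, unconnected to the 2-5% in step 3.
- **Case rule and number of examinations.** That one reading suffices is inferred. The Statistical Analysis Plan refers to five time periods and never pools cycles into an ever-OM outcome. If incidence is taken within one cycle, only the k = 5 rows apply.
- **Planning rates.** Table 2 lists the adult leukemia trial behind the 75% and 47% as using the WHO scale over 14 days. Those rates may already contain grading error, so the loss relative to plan would come only from the additional examinations.
- **Grade 1.** If pain is required as well as erythema, false readings should be rarer.
- **Photographs.** A reader might also infer that healthy mouths are absent from the calibration set. But the scale text counts grade 0 among the degrees. The mix is unspecified, which is not the same as lacking healthy mouths.

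All of this limits the size of the problem. None of it answers step 2, which needs no assumed clinical error rate, or supplies the missing case rule. Blinding makes the errors non-differential but does not remove the dilution. Daily observation after diagnosis would show one-day episodes, but nothing in the plan uses them to confirm a case.

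**Conclusion.** The concern holds as a gap in protection, not as a forecast. The calibration can pass a rater with no ability at the cut that defines the endpoint sizing the trial, and the plan has no case rule or confirmation to compensate.

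The loss in power is conditional on a single-reading rule, 5 to 15 examinations, independent errors, error-free planning rates and 46 evaluable children per group. Under these, 2% false positives per examination leave about 25-21 of 28 points (power 73-59%, from 80%), and 5% leave 22-13 points (power 62-36%). It is smaller if errors cluster within a child or are already in the planning rates. The correction is worth making because it is cheap, and the planned calibration would not reveal the problem.

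**What to change.** **Calibration.** State the share of grade 0 and grade 1 cases in the set. State the weights. Alongside the weighted kappa, report specificity on grade 0 and an unweighted kappa for grade 0 v 1 or more. Replace the range with one lower limit.

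A kappa limit of 0.80 at this cut is not enough alone. With five equal grades and no other errors, misreading 20% of healthy mouths gives 0.32·0.8/(0.2 + 0.12·0.8) = 0.865. So set a high specificity requirement on grade 0 too. A small set detects only gross failure: even with no errors, excluding a 5% false-positive rate with 95% confidence takes 59 grade 0 images (0.95^59 = 0.048).

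**Endpoint.** Write the incident-case rule: threshold, number of readings and period covered. Reconcile the two descriptions of grade 1. If pain is part of it, the calibration cases must supply that information, because a photograph cannot.

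**Analysis.** Add a sensitivity analysis that counts a case only if grade 2 or more is recorded, or grade 1 is seen again at the next daily observation. State how a missed confirming observation is handled.

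**Cost.** Some further photographs, one more kappa and one more analysis; the Summary already plans the daily observations. The confirmed-case analysis will miss true redness lasting under a day and will not remove persistent misreadings, so it belongs beside the main analysis rather than in its place.
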